11.0 Data and Specimen Management

- 11.1 AIM 1 Analysis Plan. The proposed trial uses a cluster-randomized design where the prescribing physician is the unit of randomization. We will randomize approximately 150 physicians (50 attending physicians, 100 EM resident physicians and mid-level providers) to three intervention arms (usual care, EMC², and EMC² + SMS text reminders). The estimate of 150 includes a base of 100 providers with an estimate of approximately 50 new providers over the course of the 18 months of recruitment (e.g. 15 new residents in 2015, 15 new residents in 2016 and new attending hires). At any given time, we estimate that 100 providers will be actively involved in the study, resulting in approximately 33-34 physicians per arm. Physicians will be stratified by provider role (i.e., attending vs. resident) and randomly assigned to one of the three arms with an equal number assigned to each. We will accrue approximately 12 patients per physician; we conservatively anticipate at least 54% retention for the phone call follow-up 7-14 days post prescription. These estimates will result in 1500 participants recruited with an anticipated

EHR-Based Medication Complete Communication (EMC²) Strategy to Promote Safe Opioid Use: A Physician Randomized Trial

minimum of 816 patients at in-person follow-up (272 per arm, 8 per physician) available for primary data analysis.

To ensure adequate balance across the 3 arms, potential confounders including socio-demographic characteristics, comorbidities, regimen complexity (i.e., # of medications, total pills taken daily), health literacy level, and history of opioid use will be compared using one-way ANOVA models and χ^2 tests, as appropriate. Covariates with significant differences (p -value $< .05$) across treatment groups will be included in the generalized linear mixed models (GLMMs) to adjust for the group differences as described below. We note that detected differences may be physician-specific, so if we observe differences across the treatment arms, we will explore whether the difference might be attributable to individual physicians.

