Demonstrated safe use by not exceeding the maximum dose is the primary outcome of interest for Aim 1 (H_3), with higher reported rates of provider counseling and greater understanding of risks relevant to hypotheses of secondary interest for Aim 1 (H_1, H_2). We will use GLMMs for analyses of the data, specifying the logit link function for the binary outcomes using xtmixed in Stata (v.12.1). The 3-category treatment group variable will be the independent variable of primary interest and modeled as a fixed effect with the usual care group specified as the reference. We will also include fixed effects for any potential confounding covariates noted in the descriptive studies that were not accounted for in randomization. Random effects will be included for each physician to account for intra-physician correlation among participants. For all GLMM analyses we will report point estimates and corresponding 95% confidence intervals. We will examine and report the extent to which the random effects suggest correlation of outcomes within physicians.

Measures taken to minimize bias. For the randomization scheme of this study, physician is the unit of randomization rather than patient. With healthcare interventions and quality improvement projects, such as the one proposed herein, there are no other ways to evaluate an automated EHR process than to “turn them on.” This is why the randomization will occur at the physician level rather than the patient level. This process will result in trickle down of aspects of the EMC² intervention (but not SMS texting) to patients seen by the consented provider, but not enrolled in the study for follow-up purposes (e.g., on overnight shifts).

Level of significance to be used. We will use a two-sided 5% significance test

Stopping rules. We will stop enrollment once we have reached the 1500 patient enrolled maximum.

EHR-Based Medication Complete Communication (EMC²) Strategy to Promote Safe Opioid Use: A Physician Randomized Trial

Procedures for reporting deviations from the original plan. Any deviations involving human subjects will be submitted to the IRB for review before being implemented.

Selection of subjects for inclusion in the analysis. All subjects with complete information (e.g., at least 80% completion of interview instrument) will be used in the analysis.

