EHR-Based Medication Complete Communication (EMC²) Strategy to Promote Safe Opioid Use: A Physician Randomized Trial

estimates to different proficiency levels that could arise from learning by doing.

To achieve Aim 3, [name], at UIC, will help in analyzing time and resource use related to the intervention. Any data that he would receive would be anonymous and would not contain any patient PHI. Instead, the data would involve counts of hours spent, and materials used, in creating and implementing the intervention.

11.2 Rationale for choice of sample size, power considerations. The sample size for this study was based on pairwise comparisons between the two intervention arms compared to usual care (i.e., usual care vs. EMC² and usual care vs. EMC² + SMS). This calculation was based on the primary outcome of demonstrating safe use by not exceeding the maximum recommended dose at the 7-14 day phone follow-up interview.

Conservatively estimating 54% retention rate for 7-14 day follow-up call, we will have 82% to detect a difference of 11.8% between each intervention and the usual care arm assuming a Type I error of 2.5% to account for the two comparisons. An intraclass correlation coefficient (ICC) of 0.001 was used because we do not expect patient outcomes to be influenced by the clustering of physicians due to patients being randomly assigned a physician upon ED entrance and physicians typically working a random assortment of shifts.

With the sample size set by the primary outcome of demonstrated safe use by not exceeding the maximum dose, we also show detectable effects for the secondary outcomes in Table 3, assuming at least 80% power, a Type 1 error rate of 2.5%, an ICC of 0.001, and usual care estimates from prior studies.

11.3 Data Safeguarding Procedures. Any information that could allow identification of individual patients, including the master list, will be kept strictly confidential. In order to preserve participants' confidentiality rights, research subjects will be assigned study ID numbers that will be used to identify all the information collected. A master study tracking database will contain information linking participants to their study ID numbers. This database will be on RedCap and is both encrypted and password protected and only accessible by approved study personnel at Northwestern. Grant file access permissions will only be given to specific approved research personnel, as designated by the PI.

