Statistical Analysis Plan

EHR-Based Medication Complete Communication Strategy to Promote Safe Opioid Use

NCT02431793

Document Date: June 7, 2019

Analysis Plan – Main Manuscript

Descriptive statistics were calculated for all socio-demographic, ED visit, and opioid prescription characteristics. Chi-square, one-way Analysis of Variance (ANOVA), and Wilcoxon rank-sum tests were used, as appropriate, to test for balanced randomization. An inter-cluster correlation assessment was conducted to assess the degree of independence among individuals in the same cluster. We used generalized linear mixed models on all outcomes adjusting for physician clustering. Models were run for dichotomous outcomes (safe demonstrated dosing, safe actual dosing; adjusted odds ratios [ORs] reported) and for continuous composite knowledge score (adjusted mean differences reported). Examination for possible associations between patient characteristics and outcome variables revealed significant was conducted, and all models controlled for covariates that related to the outcome. To isolate the effect of the SMS texting portion of the intervention from the EMC² EHR embedded tools a generalized linear mixed model was conducted utilizing two dummy variables (“emc2” for patients in both intervention arms, “text” for patients in EMC² +SMS arm) rather than the study arms on the primary and secondary outcomes as well as the individual knowledge or behavior questions linked to each text message. Significance for all analyses was set at $p < 0.025$ to adjust for multiple testing.

All analyses were first conducted using an intent-to-treat approach. Subsequently, because some patients did not receive one or more pieces of the intervention, the primary outcome was analyzed per-protocol, where the same methodology described previously was used but applied only to patients who successfully received all patient-facing pieces of the intervention. Patients in the EMC² arm were included in the per-protocol analysis if they received the MedSheet and the patient-centered TWS prescription wording on their bottle. Those in the EMC² +SMS arm were included in the per-protocol analysis if they received the MedSheet, TWS prescription wording on bottle, successfully enrolled in SMS texting, and received all seven text messages.

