The planned enrollment target was for 816 patients to complete the 1-2 week follow-up interval, which would have provided 80% power to detect a difference of 11.8% (from pilot data) between each of the intervention arms and the usual care arm for the primary outcome of any error on the demonstrated dosing task. All analyses were performed using SAS 9.4 (SAS Institute Inc, Cary, NC).

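### A flat 2.5% for each of the two primary contrasts is valid, but Holm would give more power at the same 5% family-wise level: a cheap improvement, not an error

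*Protocol*

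**What the plan says.** Protocol section 11.2 bases the sample size on "pairwise comparisons between the two intervention arms compared to usual care", which makes two contrasts with a shared control. It sets the level by "assuming a Type I error of 2.5% to account for the two comparisons" and states the resulting power: "we will have 82% to detect a difference of 11.8% between each intervention and the usual care arm". The analysable sample in section 11.1 is at least 816 patients, 272 per arm. The SAP gives 80% power for the same 816 patients and the same difference.

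The SAP (Analysis Plan – Main Manuscript) turns 2.5% from a sizing input into the testing rule: "Significance for all analyses was set at $p < 0.025$ to adjust for multiple testing". This is single-step Bonferroni for the two contrasts. Neither document mentions Holm, Hochberg, Dunnett or any ordered procedure.

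Two other statements bear on the point. Protocol section 11.1 says "We will use a two-sided 5% significance test" without saying whether 5% is the family level or the level per test, and it plans 95% confidence intervals for all mixed-model results. The SAP adds a second model of the primary and secondary outcomes in which two dummies, emc2 and text, replace the study arms. The same 0.025 applies there.

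**The concern.** With two tests, Holm compares the smaller p-value with 0.025 and, only if that is significant, the larger with 0.05. It controls family-wise error at 5% under any dependence between the tests and needs no extra patients and no prior ordering of the arms. The flat rule therefore gives up power on the second contrast without lowering the family-wise bound.

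This matters because the two intervention arms share all five EMC² components and differ only in the text messages. Suppose both strategies work, one contrast is clearly significant and the other has p between 0.025 and 0.05. The flat rule then calls one arm positive and the other not, and a reader could take that split as a statement about texting. Holm would declare both.

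**Working it through.** **1. The plan's own power.** Inputs: 272 per arm and 8 patients per physician (section 11.1); ICC 0.001, an 11.8-point difference and level 2.5% (section 11.2), taken as two-sided from section 11.1. The design effect is 1 + (8 − 1) × 0.001 = 1.007, so the effective n is 272 / 1.007 = 270.1 per arm. With p the usual-care rate, p̄ = p + 0.059 and z(0.9875) = 2.241:

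power = Φ{ [0.118 − 2.241 √(2p̄(1 − p̄)/n)] / √([p(1 − p) + (p + 0.118)(0.882 − p)]/n) }

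The documents give no usual-care rate for this outcome, so the 82% cannot be reproduced uniquely. Over an assumed range:

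| Usual-care rate | Power at two-sided 2.5% |
|---|---|
| 10% | 93.7% |
| 20% | 81.5% |
| 30% | 73.3% |
| 44% (minimum) | 69.3% |
| 60% | 74.4% |
| 75% | 89.6% |

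Power is 82% at a usual-care rate of 19.5% or 68.7%, and 80% at 21.5% or 66.7%. The stated figures are attainable. The comparison below is anchored on the stated 82% (or 80%) and so does not depend on the unknown rate.

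**2. Flat rule against Holm.** Treat the two test statistics as bivariate normal. With equal arms, a shared control and roughly equal variances, their correlation is (1/n) / (2/n) = 0.5. The mean that gives 82% power at 2.5% is 2.241 + z(0.82) = 2.241 + 0.915 = 3.157. Write J(a, b) for P(Z₁ > a, Z₂ > b).

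- Both declared, flat: J(2.241, 2.241) = 71.5%.
- At least one declared, either rule: 2 × 82.0 − 71.5 = 92.5%.
- One given contrast, Holm: 82.0% + J(1.960, 2.241) − J(2.241, 2.241) = 86.3%.
- Both declared, Holm: 2 × J(1.960, 2.241) − J(2.241, 2.241) = 80.2%.

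A simulation of 4 million pairs agrees. All scenarios, anchored on 82% unless stated:

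| Truth | Quantity | Flat | Holm |
|---|---|---|---|
| Both arms at planned effect | each contrast | 82.0% | 86.3% |
| | both | 71.5% | 80.2% |
| | at least one | 92.5% | 92.5% |
| Same, anchored on the SAP's 80% | each contrast | 80.0% | 84.6% |
| | both | 68.7% | 77.8% |
| | at least one | 91.3% | 91.3% |
| One at planned effect, other at half (standardised) | weaker arm | 25.4% | 34.3% |
| One works, other null | working arm | 82.0% | 82.15% |
| | null arm (false positive) | 2.5% | 4.3% |
| Both null | family-wise error | 4.65% | 4.65% |

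When both arms truly work, exactly one is declared in 92.5 − 71.5 = 21.0% of trials under the flat rule and in 92.5 − 80.2 = 12.3% under Holm. In patients, Holm would keep 82% per contrast with about 243 instead of 272 analysable per arm, about 10.5% fewer.

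**3. Sensitivity.** If power is computed from an assumed usual-care rate between 10% and 75% instead, Holm adds about 2 to 5 points per contrast and about 4 to 11 points for declaring both.

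**4. The family.** In the dummy model, emc2 is 1 in both intervention arms and text is 1 only in EMC² + SMS. The emc2 coefficient is therefore EMC² against usual care, a contrast already tested in the three-arm model; text is EMC² + SMS against EMC². If text counted as confirmatory, the family would hold three tests, the flat rule's bound would be 3 × 0.025 = 7.5%, and a step-down at 0.025 and 0.05 would no longer be correct.

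**The case against.** The strongest reply is that nothing is broken. Two tests at 2.5% hold the family at 5%, the sample size was built on that rule, and planned power and planned analysis use the same threshold. Choosing Holm over Bonferroni is a choice between valid methods. That stands, and it limits the point to an improvement.

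Three further objections also stand.

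- **The gain is a best case.** It needs both arms to work, and section 11.2 powers each contrast separately; declaring both is not a stated objective.
- **Holm has a price.** When one arm works, the false-positive risk for a null second arm rises from 2.5% to about 4.3%. The price stays inside the 5% family limit, but a reader might infer that the change costs nothing, and that is not so.
- **Intervals will conflict with the test.** Holm changes a decision only when the larger p lies between 0.025 and 0.05, and there a 97.5% interval always includes no effect. The protocol's 95% intervals do not match the flat rule either.

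Timing is the last objection. The protocol expected primary analyses by May 2017, and the SAP is dated June 2019 and written in the past tense. Loosening a threshold once results are known would be less credible than keeping the stricter rule. The documents do not say whether results were known, so the fix has to cover both cases.

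**Conclusion.** A modest and cheap improvement. The flat 2.5% is valid for the two primary contrasts but less powerful than Holm at the same family-wise level. If both arms have the planned effect, the gain is 4.3 points per contrast and 8.7 points for declaring both. The chance of any positive contrast does not change, and a single working arm gains about 0.2 points. These figures assume a correlation of 0.5 and the stated 82%; anchoring on the SAP's 80% gives 4.6 and 9.1 points.

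A reader might infer that the flat rule leaves the trial short of its planned power, or that it would misreport an arm with p between 0.025 and 0.05. The documents support neither. The power was stated at the 2.5% level, and the protocol reports estimates and intervals for every mixed model, so such a result would remain visible. Applying a prespecified threshold is not misreporting.

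**What to change.** If results were not known when the rule is changed, put this in the SAP:

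> The confirmatory family consists of the two contrasts with usual care (EMC², EMC² + SMS) on the primary outcome, estimated from the three-arm model, at a two-sided family-wise level of 5%. They are tested by Holm: the smaller p-value against 0.025 and, if significant, the larger against 0.05. The emc2/text model is supportive and outside this family. The p < 0.025 rule for other analyses does not apply to these two contrasts. The 97.5% intervals shown for them are not matched to the Holm test and may include no effect when a contrast is declared significant.

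Keep the 2.5% in the sample-size statement as the conservative single-step figure. State in the protocol that its two-sided 5% is the family-wise level, so that sections 11.1 and 11.2 agree.

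If results were already known, keep the flat 2.5% as the primary rule and show Holm only as a labelled post hoc analysis.

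The cost is one short SAP paragraph and no patients. The trade-offs are the higher false-positive rate for a null second arm and the unmatched intervals.

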12.0 Provisions to Monitor the Data to Ensure the Safety of Subjects

EHR-Based Medication Complete Communication (EMC²) Strategy to Promote Safe Opioid Use: A Physician Randomized Trial

Data Safety and Monitoring Board. The Data Safety and Monitoring Board (DSMB) will be formed in the early months of the project and be given responsibility to review and approve the study methods and analysis plan for all research aims. The DSMB members will be recruited by [name] and will include 4 local health services researchers, methodologists, and biostatisticians with related expertise. DSMB members will meet in person once a year. At these meetings the study protocol, procedures, and any issues of concern related to research integrity will be discussed. Additional meetings may be arranged for late-breaking issues. (See **Appendix** for DSMB protocol)

Adverse event monitoring. This is a behavioral interventional study. No individual administration of any therapeutic or prophylactic agent is required in this protocol and there are no procedures required by the protocol. However, because this study does involve interview questions related to the use of a medication, namely hydrocodone/acetaminophen, safety measures will be in place to detect any unsafe medication use by the patients at home. These adverse events may occur during the course of the study period from overdose (whether accidental or intentional), from abuse, from concomitant use with other products (sedatives or acetaminophen) and from withdrawal. The research assistants conducting the phone interviews and completing review of the medication diaries will have a protocol in place to identify any concerning medication use patterns with an action plan outlined if events are detected. (See attachment)

It is the expectation of the investigator that because this study is a non-invasive behavioral intervention that most, if not all, adverse events are unlikely or definitely not related to study participation or the intervention. These adverse events will be reported annually as part of regular data reporting. If any adverse events are serious or potentially study related, they would be reported as required in the time period required by the IRB.

13.0 Withdrawal of Subjects

- 13.1 In the case that subjects do not complete their follow-up phone interviews and do not respond to 3 calls attempting to re-schedule, they will be withdrawn from the study. Additionally, if subjects exhibit inappropriate or violent behavior towards research personnel, they will be withdrawn from the study.
- 13.2 If a subject decides to withdraw from the study, there will be instructions in the consent document (all patients provided signed copy) with information regarding contacting the study coordinator or PI to withdraw their consent.

EHR-Based Medication Complete Communication (EMC²) Strategy to Promote Safe Opioid Use: A Physician Randomized Trial

13.3 If a subject withdraws from the study the data collected to that time point will be retained to assess for bias in the final sample. They will not be contacted further for interviews.

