4.0 Study-Wide Number of Subjects

- 4.1 Number of Emergency Department Physicians and Mid-Level providers to be enrolled. N=150
- Number of Patients to be Enrolled. N=1500
- Number of follow up providers to be enrolled (PCP/Pharmacists) N=50

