8.0 Study Endpoints

8.1 Covariates. Baseline assessment will include a sociodemographic and health questionnaire and questions about previous use of opioids. A literacy assessment using the Newest Vital Sign (NVS) will be performed.

Primary Endpoint. Demonstrated understanding of how to properly dose the opioid medication as measured by participants' ability to correctly dose their prescription regimen using a demonstrated dosing exercise previously used in studies by both Drs. [name] and [name]. Primary endpoint will be assessed at the 7-14 day phone interview.

Secondary Endpoint. Actual use of the opioid medication as measured through the review of the medication diary, participant report of refills and new opioid prescriptions received patient opinion of the intervention as measured by both closed and open-ended questions at the time of follow-up phone interview; patient risky-behaviors while on opioids, as measured by patient self-report. Other aspects of safe use related to *risk awareness* will be assessed using a questionnaire, as will beliefs about medication use. The questionnaire will assess topics including safe storage of opioids, sharing of opioids, disposal on completion of the prescription, and questions related to possible dangerous behaviors. Secondary endpoints will be assessed with phone interviews .

Tertiary Endpoints. The identification of medication names, dosage, risks, warnings, and benefits will be assessed through a structured questionnaire that has been developed and used extensively by [name] and colleagues in multiple studies and current NIH-funded grants. The self-report of provider counseling will also be measured. Tertiary endpoint assessments will be assessed via phone interviews.

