The initial study visit (baseline) will be conducted at the time of patient enrollment. Following this baseline interview, RAs will conduct three telephone interviews (at 2-4 days post-baseline, 7-14 days post-baseline and at one month post-baseline). The first two assessments (at enrollment and 2-4day follow-up call) have been included to closely track patient recall of counseling and knowledge, while the latter two assessments (7-14 day follow-up call and 1 month follow-up call) are included to assess decay of knowledge, safe use, storage of medications and demonstrated dosing. The final call (one month post-baseline) will assess disposal of

EHR-Based Medication Complete Communication (EMC²) Strategy to Promote Safe Opioid Use: A Physician Randomized Trial

medications and determine if patients have received additional opioid pain relievers from other providers.

Baseline Interview. At the time of enrollment, the RA will ask the participant to indicate the best days and times to call within a 2-4 day range. A \$5 Gift card given to the participant for completion of enrollment tasks.

First Study (2-4 Day) Phone Call. The study phone call will be conducted at a time of convenience for the patient, however still within a 2-4 day range post-baseline. Additionally during this phone call, the RA will either confirm or schedule the 7-14 day follow-up call. A \$10 Gift card will be mailed to the participant for completion of first phone call.

Second Study (7-14 Day) Phone Call. The second phone call will be conducted at a time of convenience for the patient, however still within 7-14 day range post-baseline. Patients will be compensated for their time to complete the call with a \$20 gift card which will be mailed to the participant upon completing the call. Patients will also be asked to mail back their de-identified medication diary using the prepaid envelope provided at baseline.

Third/Final Study (1 Month) Phone Call. The final study phone call will be conducted at a time of convenience for the patient, however still within 1-month post-baseline. (See Attached Interview script)

Intervention Patients with physicians randomized to the EMC² arm will receive the 5-part EMC2 intervention.

[figure not shown]

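### The withdrawal rule in protocol sections 13.1 and 13.3 allows an unanswered 2-4 day call to close off the 7-14 day primary assessment

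*Protocol*

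**What the plan says.** Section 13.1 of the protocol provides that where subjects "do not complete their follow-up phone interviews and do not respond to 3 calls attempting to re-schedule, they will be withdrawn from the study". It names no particular interview and sets no period for the 3 calls. The same section also withdraws subjects for inappropriate or violent behaviour towards staff.

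Section 13.3 covers what follows withdrawal: "If a subject withdraws from the study the data collected to that time point will be retained to assess for bias in the final sample", and then "They will not be contacted further for interviews".

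Section 7.0 sets three follow-up calls: at 2-4 days, 7-14 days and 1 month. Section 9.0 says that the enrolment and 2-4 day assessments "have been included to closely track patient recall of counseling and knowledge". Section 8.1 puts the primary outcome at the second call: "Primary endpoint will be assessed at the 7-14 day phone interview". The two calls are linked in section 9.0, because "during this phone call, the RA will either confirm or schedule the 7-14 day follow-up call".

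On numbers, section 4.1 gives "Number of Patients to be Enrolled. N=1500", and section 11.1 says "we conservatively anticipate at least 54% retention for the phone call follow-up 7-14 days post prescription", which leads to a minimum of 816 patients (272 per arm) for the primary analysis.

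**The concern.** The 2-4 day call is not the primary assessment, but it comes first. Under the rule as written, failure to reach a patient at that call can settle whether the primary outcome is ever sought. A patient who cannot be reached on days 2-4 may well be reachable on days 7-14.

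Two things are at stake. The first is avoidable loss of primary data in a trial that already plans to lose almost half its patients by the primary time point. The second is selection after allocation. Providers are randomised before their patients are enrolled, and the SMS arm receives daily texts in the week after the prescription (section 9.2), so response to the first call could be affected by arm.

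The analysis plan does not repair such a loss. Section 11.1 analyses subjects with complete information. The SAP names intent-to-treat but describes no method for missing primary outcomes.

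**Working it through.** **1. The plan's own figure.** 1500 × 0.54 = 810. The stated 816 is 816 / 1500 = 54.4%, and 3 × 272 = 816, with 34 physicians × 8 patients = 272 per arm. The figure reproduces, allowing for rounding. The 46% expected loss is not split by cause or by call.

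**2. What the sections allow when read in order.**
- The 2-4 day call is the first follow-up interview, so it is the first at which 13.1 can apply.
- The trigger has two parts: non-completion, and no response to 3 re-scheduling calls.
- If both are met, 13.1 withdraws the patient. If 13.3 applies to that withdrawal, interview contact ends.
- The primary endpoint is collected only at the 7-14 day call, which is confirmed or scheduled during the 2-4 day call.
- Neither document says that the 7-14 day call is still attempted.

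**3. Size under assumed rates.** Let q be the share withdrawn after the 2-4 day call and r the share of those who would answer at 7-14 days if called. The documents give neither, so both are assumptions.

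Outcomes left uncollected = 1500 × q × r.

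| q | r | Outcomes | Relative to 816 |
|---|---|---|---|
| 20% | 10% | 1500 × 0.20 × 0.10 = 30 | 3.7% |
| 30% | 25% | 1500 × 0.30 × 0.25 = 112.5 | 13.8% |
| 35% | 40% | 1500 × 0.35 × 0.40 = 210 | 25.7% |

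**4. Power, in both directions.** Inputs from sections 11.1 and 11.2: 272 per arm, ICC 0.001, difference 11.8 points, type I error 2.5% per comparison (taken as two-sided). The design effect is 1 + (8 − 1) × 0.001 = 1.007, so the effective size is 272 / 1.007 = 270.1 per arm. The usual-care rate is not given. A lower rate of 19.5% is assumed because it returns the protocol's 82%.

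| Outcomes | Power if 816 is already net of the rule and these are recovered | Power if 816 ignored the rule and these are lost |
|---|---|---|
| 30 | 83.5% | 80.5% |
| 112.5 | 87.0% | 75.5% |
| 210 | 90.3% | 68.5% |

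The documents do not say which column applies.

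**5. Bias, for illustration.** With no true effect, the bias in the arm difference is about (gap in safe-dosing rate between kept and removed patients) × (difference between arms in the share removed). Assumed gaps of 10 to 30 points and removal differing by 5 to 10 points give 0.10 × 0.05 = 0.5 points up to 0.30 × 0.10 = 3.0 points, against a target difference of 11.8. If removal is equal across arms and there is no treatment effect, the bias is 0.

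**The case against.** The strongest reply is that the text is ambiguous and not plainly harmful.

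- **Which call triggers withdrawal.** Section 13.1 speaks of interviews in the plural and names none, so it could mean withdrawal only after general non-completion. That reading is possible, but it leaves the rule almost no function: participation ends with the 1-month call, and by then there is little to withdraw from. Re-scheduling also suggests one particular missed appointment.
- **Who is not contacted.** The no-contact sentence follows a clause about a subject who withdraws, directly after 13.2 on patients who choose to leave. Applying it to patients withdrawn by staff is an inference. This stands, although being withdrawn from the study would mean little if study calls continued.
- **Scheduling.** The second call is to be confirmed or scheduled, so an appointment made earlier is not excluded. The attachments, which include an appointment reminder card, may say more. This also stands.
- **Bias was considered.** Section 13.3 keeps earlier data in order to assess bias. That helps to describe who was lost, but it does not supply the missing outcome.
- **Opting out of texts.** Section 24.1 keeps patients who cancel texts in outcome assessment, so opting out does not itself trigger withdrawal. This is correct, and it is the same principle that 13.1 lacks for a missed call.

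A reader might also infer that every patient who misses the first call is dropped by about day 4, that the call works as a run-in, or that collected primary outcomes are discarded. The documents do not support this. Three unanswered calls are also required, no date for withdrawal is set, no screening on the first call is planned, and data already collected are kept.

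**Conclusion.** The concern holds as a gap in a stated rule: following sections 13.1 and 13.3 can leave obtainable primary outcomes uncollected after allocation. That the text permits this is clear. How staff applied it is not known, and it depends on 13.3 covering withdrawal by staff.

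The size cannot be computed from the documents. About 30 to 210 of 1500 patients follows from assuming that 20% to 35% are withdrawn after the first call and that 10% to 40% of those would answer later. Different loss by arm is plausible but not shown: neither document says that texts change response to calls, or that patients who are hard to reach dose less safely.

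A reader might infer that the trial is underpowered because of this rule. That does not follow. The 54% is retention at the 7-14 day call itself, is described as conservative, and may already include the loss. The point is a worthwhile and cheap improvement, and it does not invalidate the design.

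**What to change.** - Amend 13.1 so that 3 unanswered attempts close that call only, recorded as a missed assessment. The 7-14 day and 1-month calls are then still attempted for every patient, unless the patient asks to stop or the behaviour clause in 13.1 applies.
- Limit the no-contact sentence in 13.3 to those two cases.
- Schedule the 7-14 day call at baseline, so that it does not depend on completing the 2-4 day call.
- Report losses by call and by arm, separating patients who asked to stop from those who could not be reached.

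The cost is a short amendment and some extra call time for the existing research assistants. Patients can still decline at any time.

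The SAP, dated June 2019, is written in the past tense. If follow-up is complete, the amendment cannot recover outcomes. In that case the report should state how 13.1 was applied, give the losses by call and arm, and add a sensitivity analysis for missing primary outcomes.
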